#### **3.2.3.1 Procedure Success Rate**

The procedure success rate is defined to be the percentage of aneurysms in which coil mass position is maintained within the sac with parent artery patency, without additional procedures for treatment of the aneurysm since the index procedure. The procedure success rate will be summarized immediately post-treatment (acute), and at the 6 and 12 month follow-up assessments.

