## 9.5 Handling of Missing Data

Primary effectiveness and primary safety endpoint analyses will be conducted on the modified intent-to-treat (MITT) population, where subjects with missing data at the time of endpoint analysis will be imputed as last observation carried forward (LOCF); see Section 9.8 for analysis set definitions. Note that the immediate post-procedure evaluation will be utilized in this LOCF methodology if this is the last observation on file. MITT subjects who receive the device but in whom there is no post-procedure data will be treated as failures for the purpose of the primary effectiveness endpoint analysis; these subjects will be excluded from all other endpoint analyses. Subjects who do not receive the device because of treatment failure due to reasons associated with the device will also be treated as failures for the primary effectiveness endpoint analysis; these subjects will be excluded from all other endpoint analyses. MITT subjects who do not receive the device because of an intra-operative surgeon decision based on patient anatomy (e.g. vessel tortuosity) will be treated as missing (and not as failures) in all endpoint analyses, including the primary effectiveness and primary safety endpoint analysis.

All subjects who have died prior to an evaluation will have a mRS score of 6 imputed for that time point for analysis purposes.

All other analyses based upon MITT or PP population data will be based upon actual data, with no data imputation.

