### **Secondary Endpoints**

#### **Secondary Effectiveness Endpoints:**

**Procedure Success:** Procedure Success is defined as the percentage of aneurysms in which coil mass position is maintained within the sac with parent artery patency, without additional procedures for treatment of the aneurysm since the index procedure. Procedure success will be summarized immediately post-treatment (acute), and at the 6 and 12 month follow-up assessments.

**Acute and 6 Month Complete Aneurysm Occlusion as per the Raymond Scale:** The percentage of aneurysms in which a score of 1 (complete obliteration) is achieved on the Raymond Scale immediately post-procedure (acute) and at the 6 month follow-up angiographic assessments, respectively, will be evaluated.

**Complete/Partial Aneurysm Occlusion as per the Raymond Scale:** The percentage of aneurysms in which a score of 1 (complete obliteration) or 2 (residual neck) is achieved on the Raymond Scale immediately post-procedure (acute), and at the 6, and 12 month follow-up angiographic assessments will be evaluated.

**Percent Aneurysm Occlusion:** The percentage of aneurysms with occlusion of 100%, 90%-99%, 70-89%, 50-69%, 25-49%, or <25% occlusion in accordance with Consensus Grades 0-5, respectively, will be summarized immediately post-procedure (acute), and at 6 and 12 month follow-up, respectively.

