### **ACUTE PROCEDURE SUCCESS**

The percentage of aneurysms in which complete coverage across the aneurysm neck is achieved and for whom coil mass position is maintained within the sac with parent artery patency without additional procedures for treatment of the aneurysm since the index procedure, as assessed immediately post-treatment.

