## **PROCEDURE SUCCESS**

The percentage of aneurysms in which complete coverage across the aneurysm neck is achieved and for whom coil mass position is maintained within the sac with parent artery patency without additional procedures for treatment of the aneurysm since the index procedure, as assessed post-procedure.

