5.2 Secondary Endpoints

5.2.1 Secondary Effectiveness Endpoint

- Procedure success rate

The procedure success rate is defined to be the percentage of aneurysms in which coil mass position is maintained within the sac with parent artery patency, without additional procedures for treatment of the aneurysm since the index procedure. The procedure success rate will be summarized immediately post-treatment (acute), and at the 6-Month and 12-Month Follow-up assessments.

- Complete aneurysm occlusion as per the Raymond Scale

The percentage of aneurysms in which a score of 1 (complete obliteration) is achieved on the Raymond Scale immediately post-procedure (acute) and at the 6-Month and 12-Month Follow-up angiographic assessments, respectively, will be evaluated.

- Complete/partial aneurysm occlusion as per the Raymond Scale

The percentage of aneurysms in which a score of 1 (complete obliteration) or 2 (residual neck) is achieved on the Raymond Scale immediately post-procedure

(acute), and at the 6-Month and 12-Month Follow-up angiographic assessments will be evaluated.

- Percent aneurysm occlusion

The percentage of subjects with aneurysms occlusion of 100%, 90%-99%, 70-89%, 50-69%, 25-49% or <25% occlusion in accordance with Consensus Grades 0-5, respectively, will be summarized immediately post-procedure (acute), and at the 6 and 12-Month Follow-up, respectively.

- Recanalization rate

The percentage of aneurysms in which recanalization is documented at any time up to and including the 12-Month Follow-up visit, will be evaluated. Recanalization will be defined as an increase in aneurysm filling as compared to the previous study-specified angiographic assessment, resulting in a change in (i.e., worsening of) the Raymond classification. Changes in Raymond Scale will be classified as stable, improved, or recanalized based on the follow-up angiograms.

- Retreatment rate

The percentage of target aneurysms that are retreated at any time up to and including the 12-Month follow-up visit will be evaluated. Retreatment will be defined as any additional treatment of the target aneurysm after the index procedure (retreatment includes staged procedures), or an additional procedure (regardless of whether retreatment is by surgery or endovascular treatment) due to recanalization, rupture or bleeding.

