5.4 Safety Follow-up after 12 Months Post-Procedure

According to the Close Out Plan, all enrolled and treated subjects will be required to complete follow-up visits through 12 months post-procedure. Hence, only a small number of subjects will have additional safety follow-up data post 12 months. AEs that started after 12-month follow-up will only be listed.

6. Levels of Significance

Protocol specified tests of hypotheses of the primary endpoints at the planned 2.5% significance level will not be conducted due to early termination of the study prior to enrollment of the planned sample size. Two-sided confidence intervals will be computed at a 95% confidence level but are not intended for inference.

7. Analysis Sets

The following analysis sets are defined for the study.

- Modified Intent-to-Treat (mITT) Analysis Set

The mITT Analysis Set consists of all consented (enrolled) subjects who meet all pre-procedure angiographic eligibility criteria, and in whom treatment with the Enterprise device is attempted.

8. Sample Size Justification

This study was originally planned at a total sample size N=320, with an interim analysis for an early stop (either due to futility or tentative success) at N=160 when subjects were enrolled and followed for a minimum of 6-month post-procedure.

However, as the study will be terminated early due to low enrollment, the total sample size for the descriptive analyses in the final CSR will be based on the actual enrollment achieved. .

9. Data and Safety Monitoring Board (DSMB)

An independent DSMB was constituted for monitoring the accumulated interim data as the study progresses to ensure subject safety. All safety review procedures were established and agreed upon in the DSMB Charter prior to enrollment of the first subject.

10. Analyses to be Conducted

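### Procedure success has two conflicting definitions, and under either the SAP wording or protocol 9.5 a device-related failure to implant ENTERPRISE that is coiled in the same session does not lower the rate

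*SAP*

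**What the plan says.** **Definition in the SAP and the protocol body.** SAP 5.2.1 counts "the percentage of aneurysms in which coil mass position is maintained within the sac with parent artery patency", provided no further procedure has been done on the aneurysm since the index session. SAP 10.4.2.1 adds no other condition. Protocol 3.2.3.1 ("The procedure success rate is defined to be the percentage of aneurysms in which coil mass position is maintained within the sac with parent artery", which must be patent) and protocol 9.6 ("Procedure Success is defined as the percentage of aneurysms in which coil mass position is maintained within the sac with parent artery patency") say the same, as does the synopsis.

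**Definition in Appendix 1.** The Procedure Success entry requires that "complete coverage across the aneurysm neck is achieved and for whom coil mass position is maintained within the sac", together with patency and no additional procedure. The Acute Procedure Success entry opens in the same way: "The percentage of aneurysms in which complete coverage across the aneurysm neck is achieved".

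**Who is counted.** The mITT set in SAP section 7 takes angiographically eligible subjects "in whom treatment with the Enterprise device is attempted". SAP 10.4.2 summarises all secondary endpoints on that set. It names one failure rule, which is retreatment (including staged procedures) on or before the imaging assessment.

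**Subjects without an implanted device.** Protocol 9.5 counts subjects who did not receive the device for device-related reasons as failures for primary effectiveness, and adds that "these subjects will be excluded from all other endpoint analyses". It treats those not implanted because of anatomy as missing in every analysis. The SAP neither repeats nor revokes these rules. SAP 10.6 says only that missing data are not imputed and percentages use non-missing data.

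**The concern.** One named endpoint has two definitions, and the SAP does not say which governs. The version it carries forward mentions neither neck coverage nor a stent. The set on which it is computed includes attempts that ended without an implant.

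Failure to deliver the stent is foreseeable: protocol 10.1.1 lists it as an anticipated event, and Appendix 1 gives failure to deploy as an example of a device-related technical complication. If such an aneurysm is coiled in the same session, a reader would expect the case to count against procedure success. The plan either counts it in favour or removes it. The reported percentage would then be biased upward relative to success among all attempts. Because SAP 10.1 limits the output to descriptive statistics, the percentage is itself the result, with no test behind it.

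**Working it through.** No figure is stated for this endpoint (no target, power or sample size), so there is nothing to reproduce. The check is textual, followed by an illustration of size.

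**Step 1: follow one case through the text.** Take an eligible subject in whom ENTERPRISE is attempted, the stent cannot be deployed for a device-related reason, and the sac is coiled in the same session. The coils stay in place and the artery stays open.

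- Analysis set: the attempt is enough for mITT (SAP section 7).
- Additional procedure: Appendix 1 defines the index procedure as the session in which stenting is attempted, so same-session coils are not a later procedure or retreatment.
- Missing data: the post-treatment angiogram can be read, so the case is not missing in the ordinary sense of SAP 10.6.
- Literal SAP reading: all conditions are met, so the case is a **success**.
- Protocol 9.5, if still in force: the case is **excluded**.
- Appendix 1: complete neck coverage is required. If coverage means coverage by the stent, the case is **not a success**.

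**Step 2: size.** Let n be the number of attempts, f the number of such coil-only rescues, and s the successes among the n − f implanted subjects.

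- A, literal SAP: (s + f)/n
- B, protocol 9.5 exclusion: s/(n − f)
- C, non-implants counted as not a success: s/n

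The differences are A − C = f/n; B − C = (f/n) × s/(n − f); and A − B = (f/n) × [1 − s/(n − f)].

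The documents give neither actual enrolment nor the number of failed attempts. The inputs below are assumptions: n = 50, about 90% success among implanted subjects, and f = 1, 3 or 5 (2%, 6%, 10%).

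| f | s | A | B | C | A − C | B − C | A − B |
|---|---|---|---|---|---|---|---|
| 1 | 44 | 45/50 = 90.0% | 44/49 = 89.8% | 44/50 = 88.0% | 2.0 | 1.8 | 0.2 |
| 3 | 42 | 45/50 = 90.0% | 42/47 = 89.4% | 42/50 = 84.0% | 6.0 | 5.4 | 0.6 |
| 5 | 40 | 45/50 = 90.0% | 40/45 = 88.9% | 40/50 = 80.0% | 10.0 | 8.9 | 1.1 |

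Differences are in percentage points. The two readings the plan allows (A and B) lie close together, and both lie above C. The illustration leaves out implanted subjects with incomplete neck coverage. They would lower an Appendix 1 rate further, by an amount the documents do not give.

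**The case against.** **The SAP did not create the omission.** A reader might infer that the SAP departed from the protocol. It did not: its definition matches the protocol body, and the conflict is already inside the protocol. Appendix 1 may also be out of date, since its percent-occlusion categories differ from the Consensus Grades used in the body and the SAP. This stands. The documents do not establish that the Appendix 1 version is the right one.

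**Counting the case as a success is not settled.** A reader might infer that coil-only rescues will certainly be successes. That requires reading the SAP's silence as dropping protocol 9.5. There is some support for that reading: SAP 10.4.1.1 replaces last-observation-carried-forward with exclusion of missing values, and the SAP states exclusions for several other endpoints but none for procedure success. It is still an inference. What survives is that a device-related non-implant coiled in the same session lowers the rate under neither reading.

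**The endpoint is not blind to every device failure.** A deployed stent that fails to hold the coils, an occluded parent artery, or a rescue in a later session does lower the rate. Protocol 9.10.3 also lists attempted and successful procedures, and protocol 10.7 requires malfunctions to be documented. These show delivery failures elsewhere but do not correct this percentage. The SAP also does not carry over the per-protocol set, which required receipt of the device.

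**Appendix 1 does not name an implanted ENTERPRISE.** It implies one only through neck coverage. The European feasibility study (protocol 1.3.1) did define procedural success through stent placement with complete neck coverage, but that definition is not written into this trial.

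**The earlier studies do not size the gap.** A reader might combine the registry figures in protocol 1.3.4 (85.7% placement, 83.5% coil position) into a joint rate as low as 0.857 + 0.835 − 1 = 69.2%, a gap of up to 83.5 − 69.2 = 14.3 points. This fails. On the 105 subjects reported, 83.5% is not attainable (87/105 = 82.9%, 88/105 = 83.8%), so the denominators differ. The registry's coil-position measure also already presupposes that ENTERPRISE is holding the coils. In the US study placement with satisfactory coil position was 100%. In Argentina the two measures differed in one of ten subjects, because of image quality.

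**Conclusion.** The point holds in this form: procedure success is defined in two incompatible ways, and a device-related non-implant coiled in the same session is either a success (literal SAP) or removed (protocol 9.5). It never counts against the rate.

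Compared with counting such cases as not a success, the literal SAP reading is higher by f/n, which is 2 to 10 points for an assumed 2% to 10% of attempts. The 9.5 exclusion is higher by f/n times the success rate among implanted subjects: 1.8 to 8.9 points in the example. These sizes rest on assumed counts and on every rescue retaining its coils with a patent artery.

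The consequence is limited. The endpoint is secondary and descriptive in a study closed early for low enrolment, and no test, power figure or success criterion depends on it. It is still worth correcting, because the bias has a known direction and the remedy is mostly wording.

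**What to change.** 1. Reconcile SAP 5.2.1 and 10.4.2.1, protocol 3.2.3.1 and 9.6 (with the synopsis), and Appendix 1 on one definition, stating explicitly whether neck coverage is required.
2. State in the SAP that mITT subjects who did not receive ENTERPRISE for device-related reasons are not procedure successes. This matches how protocol 9.5 already treats them for primary effectiveness. Amend the 9.5 exclusion so that it no longer covers this endpoint.
3. Report the number of anatomy-based non-implants separately, and show the rate both excluding them and counting them as failures.

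**Cost.** Items 2 and 3 need SAP wording, a matching line in protocol 9.5 and the recorded reason for each non-implant. The reported rate may be slightly lower. If neck coverage is kept in item 1, the core laboratory must read it. Protocol 6.2.4 already sends post-treatment images to the study image system, but the documents do not show that a coverage reading is recorded, so that should be confirmed first.

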5.2.2 Secondary Safety Endpoints

- Rate of new neurological deficits as per the modified Rankin Scale (mRS)

New neurological deficits will be evaluated in terms of mRS scores at baseline (pre-procedure) and follow-up (30 days, 6-Month and 12-Months post-procedure).

- NIH Stroke Scale (NIHSS) total score

Neurological morbidity will be assessed using the NIHSS total score. The NIHSS, administered by the investigator, is a 15-item scale used to evaluate the effect of acute cerebral infarction on the levels of consciousness, language, neglect, visual-field loss, extraocular movement, motor strength, ataxia, dysarthria, and sensory loss. A trained observer rates the subject's ability to answer questions and perform activities. Ratings for each item are scored on either zero to three or zero to five (with 0 as normal).

- Adverse events (AEs) and clinical complications

AEs including complications associated with an untoward medical occurrence, from the start of the index procedure until completion of the 12-Month Follow-up will be evaluated, including serious adverse events (SAEs), device- or procedure-related AEs, unanticipated adverse device effects (UADEs) and deaths.

- Reduced TICI flow

The percentage of target aneurysms in which a new occurrence of unintentional and persistent reduced TICI flow (TICI score of 0 or 1) is observed at the target vessel during the index procedure as a result of a mechanical obstruction such as dissection or luminal thrombus will be evaluated.

- Bleeding complications

The number and percentage of subjects who experience a procedure related hemorrhagic event which requires any of the following will be evaluated: blood transfusion, surgical intervention, a new hospitalization, or lengthening of hospital stay. The complications of hematoma requiring treatment (i.e., a hematoma > 5 cm in diameter occurring at the access site) and retroperitoneal bleeding will be reported as hemorrhagic events.

- In-stent stenosis

The percentage of aneurysms in which in-stent stenosis is documented immediately post-procedure (acute) and up to and including 6 months post-procedure, will be evaluated.

Acute in-stent stenosis will be further characterized by whether it results from vasospasm, and whether the vasospasm was responsive to medication.

- Thrombosis

The percentage of aneurysms in which thrombosis is documented up to and including 6 and 12 months post-procedure will be evaluated. Thrombosis is defined as in-stent thrombosis.

5.3 Ancillary Endpoints

- Stent movement/migration

Stent movement and/or migration will be evaluated from the start of the index procedure until completion of the 12-Month Follow-up.

5.4 Safety Follow-up after 12 Months Post-Procedure

According to the Close Out Plan, all enrolled and treated subjects will be required to complete follow-up visits through 12 months post-procedure. Hence, only a small number of subjects will have additional safety follow-up data post 12 months. AEs that started after 12-month follow-up will only be listed.

6. Levels of Significance

Protocol specified tests of hypotheses of the primary endpoints at the planned 2.5% significance level will not be conducted due to early termination of the study prior to enrollment of the planned sample size. Two-sided confidence intervals will be computed at a 95% confidence level but are not intended for inference.

7. Analysis Sets

The following analysis sets are defined for the study.

- Modified Intent-to-Treat (mITT) Analysis Set

The mITT Analysis Set consists of all consented (enrolled) subjects who meet all pre-procedure angiographic eligibility criteria, and in whom treatment with the Enterprise device is attempted.

8. Sample Size Justification

This study was originally planned at a total sample size N=320, with an interim analysis for an early stop (either due to futility or tentative success) at N=160 when subjects were enrolled and followed for a minimum of 6-month post-procedure.

However, as the study will be terminated early due to low enrollment, the total sample size for the descriptive analyses in the final CSR will be based on the actual enrollment achieved. .

9. Data and Safety Monitoring Board (DSMB)

An independent DSMB was constituted for monitoring the accumulated interim data as the study progresses to ensure subject safety. All safety review procedures were established and agreed upon in the DSMB Charter prior to enrollment of the first subject.

10. Analyses to be Conducted

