#### ***Assessment and subject interview***

- Vital Signs (Blood pressure, Heart Rate, and Respirations)
- Relevant Concomitant Medications (since 18 month follow-up): indicate any antithrombotics (including anti-platelets, anticoagulants, and fibrinolytics) and inhibitors of ADP-induced platelet aggregation medications administered more than 24 hours post-procedure through end of study participation
- Neurological evaluations performed by qualified personnel. Included as part of this examination are the NIH Stroke Scale Score, Modified Rankin Scale, clinical neurological evaluation, and, if applicable, the Hunt and Hess Scale (HHS) for subarachnoid hemorrhage
- MRI/MRA or angiogram (an angiogram must be performed if any stent or coils are not MRA/MRI compatible) to assess for in-stent stenosis, thrombosis and hydrocephalus, or if an angiogram is

- performed to assess for in-stent stenosis and thrombosis, then also obtain MRI or CT to assess for hydrocephalus)
- Event assessment (since 18 month follow-up) (i.e. adverse events, protocol deviations, device malfunction/product complaint)

Following the 24 month study visit, the subject will be discharged from the study. However, if the investigator determines there are indications of delayed hydrocephalus or in-stent stenosis occurring, additional follow-up may be required, including MRI or CT at the Investigator's discretion. If this should occur the investigator will determine the additional follow-up required at that time and inform the study sponsor.

If a subject presents with an adverse event at the 24 month follow-up, he/she will receive appropriate treatment for that condition. If the subject's condition precludes him or her from undergoing any 24 month evaluation specified by the protocol, the subject would be discharged from the study after the Investigator documents in the subject's medical record that a stable clinical endpoint has been reached, or that the subject's status is not associated with the device or procedure.

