#### **9.10.6 Supplemental Safety Follow-up Report on Continued Follow-up Subjects**

A supplemental safety follow-up report will be written to summarize safety outcomes for CF subjects through the 2 year follow-up evaluation. There are no formal primary or secondary endpoints regarding these outcomes.

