10.4 Primary and Secondary Endpoint Analyses.....	10
10.4.1 Primary Endpoints	10
10.4.2 Secondary Endpoints	11
10.4.3 Ancillary Endpoint Analyses.....	13
10.4.4 Safety Follow-up through 24 months post-procedure	14
10.5 Plans for Interim Analysis	14
10.6 Handling of Missing Data	14
10.7 Sensitivity Analyses	14
10.8 Subgroup Analysis.....	14
10.9 Assessment of Site Homogeneity	14
10.10 Additional Endpoint Analyses.....	14
11. Appendix: Tables, Listings and Graphs Shells	15

1. Study Design

This is a prospective, multi-center, single arm, clinical study to evaluate the safety and effectiveness of the ENTERPRISE stent when used in conjunction with endovascular coil embolization in the treatment of unruptured wide-neck, intracranial, saccular anterior circulation aneurysms (≤ 10 mm) arising from a parent vessel with a diameter of ≥ 2.5 mm and ≤ 4 mm. Due to low enrollment in the study, the Sponsor has decided to terminate the study early. The details regarding the length of follow-up for ongoing subjects are documented in the Close Out Plan.

2. Treatment Assignment

This is a single arm study with no comparator device, eligible subjects are expected to be treated with any of the following study devices.

- ENTERPRISE® Vascular Reconstruction Device and Delivery System (ENTERPRISE VRD system),
- ENTERPRISE® 2 Vascular Reconstruction Device and Delivery System (ENTERPRISE 2 VRD system).

3. Randomization and Blinding Procedures

No randomization or blinding is applied in the study.

4. Interval Windows

The following analysis intervals will be applied on the study.

Table 1: Analysis Intervals for Assessments

Visit	Description	Analysis Interval
Screening/Baseline	Screening/Baseline	Day -14 – Day 0
Immediate Pre-Procedure	Immediate prior to treatment	Within 12 hours prior to procedure
Index Procedure	Treatment	Day 0
Immediate Post-Procedure	Immediate post treatment	Within 12 hours post-procedure
Hospital Discharge	Hospital discharge	12 hours to 36 hours post-procedure
30-Day Follow-up	Telephone interview	Day 10 – Day 60
6-Month Follow-up	Clinic visit & Angiogram	Day 92 – Day 240
12-Month Follow-up	Clinic visit & Angiogram	Day 270 – Day 450
18-Month Follow-up	Telephone interview	Day 457 – Day 592
24-Month Follow-up	Clinic visit & MRA or Angiogram	Day 685 – Day 775

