10.4.2.2 Secondary Safety Endpoints

- Rate of new neurological deficits as per mRS

The number and percentage of subjects with new neurological deficits, not related to stroke or death, will be summarized at baseline (pre-procedure) and follow-up visits, e.g., 30 days, 6 and 12 months post-procedure. Subjects who died prior to an evaluation will have an mRS score of 6 imputed at that timepoint for analysis purpose.

- NIHSS total score

The NIHSS total score and its change from baseline will be summarized at baseline (pre-procedure) and follow-up visits (6 months and 12 months post-procedure). In addition, the number and percentage of subjects who show a worsening from baseline (an increase of 4 points or more) will also be presented. Only the observed scores will be included in summaries.

- Adverse Events and Clinical Complications

AEs from the start of the index procedure until completion of the 12-Month Follow-up will be coded using the latest version of Medical Dictionary for Regulatory Activities (MedDRA) into system organ class (SOC) and preferred terms (PTs). The number of events, the number and percentage of subjects with events and event rates by SOC and PT will be summarized for the following:

- Any AEs
- Study device or procedure related AEs
- Any serious AEs (SAEs)
- Unanticipated AEs
- AEs leading to death

AEs related to device/procedure are defined as those with the relationship of definitely, probably or possibility related. AEs with miss relationship will not be imputed. Subjects with multiple relationships on the same AE will be reported by the events of the highest relationship. Only the relationship as determined by CEC will be used in the safety analysis.

In addition, device or procedure related AEs will be presented overall and by study period as follows:

Table 2: AEs by Study Period

Study Period	Lower Bound of AE Start Date	Upper bound of AE Start Date
Peri-procedure	from the beginning of the procedure	Until 24 hours post-procedure (Day 0)
12-Month Follow-up	After 24 hours post-procedure (i.e., from Day 1)	Until the date of: 
○ early discontinuation in the study; or

Study Period	Lower Bound of AE Start Date	Upper bound of AE Start Date
		
 ○ the upper bound of the 12-Month analysis window (i.e., Day 450)

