10.4.4 Safety Follow-up after 12 months post-procedure

AEs that started post the upper bound of 12-Month follow-up (i.e., after Day 451) will be listed.

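### After 12 months the SAP specifies only an adverse event listing: it names no output for 24-month imaging, NIHSS, 18- and 24-month mRS or later retreatments, and the Day 450/451 boundary is inconsistent

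*SAP*

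**What the plan says.** SAP 5.4 explains that, under the Close Out Plan, treated subjects need to complete follow-up only through 12 months. It draws the consequence "Hence, only a small number of subjects will have additional safety follow-up data post 12 months" and then gives the reporting rule: "AEs that started after 12-month follow-up will only be listed". SAP 10.4.4 restates the rule with a day number: "AEs that started post the upper bound of 12-Month follow-up (i.e., after Day 451) will be listed". In SAP 10.4.2.2, Table 2 closes the 12-month AE period at early discontinuation or at "the upper bound of the 12-Month analysis window (i.e., Day 450".

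SAP Table 1 sets the 12-month window at "Day 270 – Day 450". It keeps an 18-month window ("Day 457 – Day 592") and a 24-month window (Day 685 to Day 775).

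The protocol plans more for this period. The 18-month contact (6.3.7) may be by telephone and includes mRS. The 24-month visit (6.3.8) includes mRS, NIHSS and imaging "to assess for in-stent stenosis, thrombosis and hydrocephalus". Section 7 adds a core-laboratory Raymond reading at 24 months. Section 9.8 plans clinical outcome and safety summaries for the continued follow-up set, and 9.10.6 says: "A supplemental safety follow-up report will be written to summarize safety outcomes for CF subjects through the 2 year follow-up evaluation". Section 9.11 plans to submit the data out to 24 months as a post-approval report.

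**The concern.** Two things looked wrong. First, the SAP keeps the 18- and 24-month windows but attaches no analysis or listing to them. Either outputs were left out or the windows are leftovers, and the text does not say which. If the SAP is followed as written, a stenosis, a re-opened sac or a worsened mRS found after 12 months is reported only if a site also recorded it as an AE.

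Second, two sections give different days for the end of the 12-month AE period and the start of the later listing, so an event could fall between them.

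At stake is whether the report can say anything about late device performance, even in a handful of subjects, and whether each late AE has one defined place.

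**Working it through.** **1. What is scheduled after 12 months against what the SAP names.**

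| Item | Protocol, after 12 months | Last time point named in the SAP |
|---|---|---|
| In-stent stenosis | 24 months (6.3.8) | 12 months (10.4.1.2) |
| In-stent thrombosis | 24 months (6.3.8) | 12 months (10.4.2.2) |
| Raymond class | 24 months, core laboratory (7) | 12 months (10.4.1.1, 10.4.2.1) |
| Hydrocephalus | 24 months (6.3.8) | none |
| NIHSS | 24 months (6.3.8) | 12 months (10.4.2.2) |
| mRS | 18 and 24 months (6.3.7, 6.3.8) | 12 months, visits given as examples (10.4.2.2) |
| Retreatment | retreated subjects followed for safety to 24 months (4.0) | 12 months (10.4.2.1) |
| AEs | 18 and 24 months | listing (5.4, 10.4.4) |

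Only the AE row has a specified output after 12 months. The continued follow-up set is also gone: SAP Section 7 defines mITT alone.

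**2. Can the AE listing stand in for the rest?** Protocol 10.1.2 and Appendix 1 state that recanalization is not an AE. Protocol 10.1.1 nevertheless includes recanalization or regrowth among anticipated adverse events, so whether a late case is entered depends on which section a site follows. Stenosis of the stented segment and stent thrombosis are in the 10.1.1 list with no contrary statement, so some of these would be captured. In every case a listing of events has no denominator: an empty listing does not separate subjects imaged and clear from subjects not imaged.

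**3. The day boundary.** Inputs: the index procedure is Day 0 (SAP 10.1); Table 2 ends on Day 450; the listing parenthesis in 10.4.4 says after Day 451; the last window ends on Day 775.

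- Parenthesis read literally: Days 0 to 450 are tabulated and Days 452 to 775 are listed. Uncovered: Day 451, one day.
- Main clause of 10.4.4 (after the upper bound, Day 450): Days 451 to 775 are listed. Uncovered: none. Counted twice: none.

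So the sentence contradicts its own parenthesis, and starting after Day 450 resolves it.

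**4. A related ambiguity.** Table 2 is introduced for device- or procedure-related AEs. The other AE summaries in 10.4.2.2 end when the 12-month follow-up is complete, with no day given. If that means the actual visit day *v*, and the listing starts on Day 452, the uncovered days run from *v* + 1 to 451, a length of 451 − *v*:

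| Assumed visit day | Uncovered days | Length |
|---|---|---|
| 270 (SAP window opens) | 271–451 | 181 |
| 320 (protocol window opens) | 321–451 | 131 |
| 360 (12 × 30 days) | 361–451 | 91 |
| 410 (protocol window closes) | 411–451 | 41 |
| 450 (SAP window closes) | 451 | 1 |

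Correcting 451 to 450 alone shortens each gap by one day, to 450 − *v*. Closing it fully requires the same Day 450 cut-off in all 12-month AE tables.

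**The case against.** The strongest reply is that the SAP made an open and reasonable choice. The study stopped early, the report is descriptive, and SAP 5.4 gives the small number of subjects as its reason. Protocol 9.6 sets no formal endpoints at 24 months. The four outcomes it itemises for the supplemental report (all AEs, rupture, major ipsilateral stroke, parenchymal hemorrhage) are all AEs, so the listing covers them. This stands, and it limits the weight of the point. It does not explain why imaging and neurological results go unlisted: small numbers argue against rates, not against a listing.

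It can also be said that outputs may exist elsewhere. SAP Section 4 summarises tables by Table 1 visit unless specified otherwise, the mRS visits are given as examples, 10.1 allows listings, and the shells are a separate document. That is fair. A reader might infer that these results were collected and will appear nowhere. The documents do not support that: they do not say which late assessments were done, and neither the shells nor the Close Out Plan is available here. What can be shown is that the SAP text names no output.

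Two other tempting readings fail. The gap does not extend to 18-month imaging or NIHSS, because neither is scheduled then. Nor does the 15% figure for stenosis measure what could go unseen. It is the limit for an upper 95% confidence bound at 12 months (Protocol 9.7), not a permitted rate. At the planned 150 evaluable subjects, 15/150 gives 0.100 + 1.96 × √(0.100 × 0.900/150) = 0.148, which passes, and 16/150 gives 0.156, which fails. The SAP has dropped that test, and the figure says nothing about late events.

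**Conclusion.** The point holds, at small size. The SAP specifies only an AE listing after 12 months and names no output for 24-month imaging, Raymond class, NIHSS, 18- and 24-month mRS or later retreatments. The AE listing cannot be relied on for late recanalization and gives no number assessed.

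The Day 451 gap is a one-day inconsistency arising from a parenthesis. A reader might infer that such events are certainly lost, but the main clause of 10.4.4 would include them. The wider range of 1 to 181 days applies only if the general AE tables stop at the actual visit while the listing starts on Day 452. It matters only for subjects still followed after that visit.

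The number of subjects affected is not stated beyond being small, and no conclusion on a formal endpoint changes. The documents also do not show that the final report will be the study's only report, since neither says whether the protocol's 24-month report was cancelled.

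**What to change.** - In SAP 5.4 and 10.4.4, add one by-subject listing, with the number of subjects assessed for each item, of whatever data exist on 18-month mRS; 24-month mRS, NIHSS, in-stent stenosis, thrombosis, Raymond class and hydrocephalus; and later retreatments. If any of these are deliberately omitted, say so and give the reason.
- In 10.4.4, change the day in the parenthesis from 451 to 450.
- In 10.4.2.2, apply the Day 450 cut-off to every AE table that covers the 12-month follow-up, so that tables and listing meet without gap or overlap.

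The cost is one extra listing and two wording edits. No new data collection is needed, since the listing covers only data that exist.
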